6.0 CRITERIA FOR SUBJECT ELIGIBILITY

Describe the characteristics of the patient/subject population.

6.1 Subject Inclusion Criteria

- Newly diagnosed patients with histologically confirmed MM based on the following criteria:
 - Clonal plasma cells in the bone marrow
 - Measurable disease within the past 4 weeks defined by any one of the following:
 - Serum monoclonal protein ≥ 1.0 g/dL
 - Urine monoclonal protein >200 mg/24 hour
 - Involved serum immunoglobulin free light chain > 10 mg/dL AND abnormal kappa/lambda ratio
- Evidence of underlying end organ damage and/or myeloma defining event attributed to underlying plasma cell proliferative disorder meeting at least one of the following:
 - Hypercalcemia: serum calcium >0.25 mmol/L (> 1 mg/dL) above upper limit of normal or ≥ 2.75 mmol/L (11 mg/dL)
 - Anemia: hemoglobin value <10 g/dL or > 2 g/dL below lower limit of normal
 - Bone disease: ≥ 1 lytic lesions on skeletal X-ray, CT, or PET-CT. For patients with 1 lytic lesion, bone marrow should demonstrate $\geq 10\%$ clonal plasma cells
 - Clonal bone marrow plasma cell percentage $\geq 60\%$
 - Involved/un-involved serum free light chain ratio ≥ 100 and involved free light chain >100 mg/L.
 - > 1 focal lesion on magnetic resonance imaging study (lesion must be >5 mm) in size
- Creatinine Clearance ≥ 60 ml/min. CrCl can be measured or estimated using Cockcroft-Gault method, MDRD, or CKD-EPI formulae
- Age ≥ 18 years at the time of signing the informed consent documentation
- Eastern Cooperative Oncology Group (ECOG) performance status 0-2
- Absolute neutrophil count (ANC) ≥ 1.0 K/uL, hemoglobin ≥ 8 g/dL, and platelet count ≥ 75 K/uL, unless if cytopenias are deemed to be due disease at discretion of clinical investigator. Transfusions and growth factors are permissible.
- Adequate hepatic function, with bilirubin < 1.5 x the ULN, and AST and ALT < 3.0 x ULN.

- All study participants must be able to tolerate one of the following thromboprophylactic strategies: aspirin, low molecular weight heparin or warfarin (coumadin) or alternative anti-coagulant.
- All study participants must be registered into the mandatory eREMS® program, and be willing and able to comply with the requirements of REMS®.
- Females of childbearing potential (FCBP)[†] must have a negative serum or urine pregnancy test within 10 – 14 days and again within 24 hours prior to prescribing lenalidomide for Cycle 1 (prescriptions must be filled within 7 days) and must either commit to continued abstinence from heterosexual intercourse or begin TWO acceptable methods of birth control, one highly effective method and one additional effective method AT THE SAME TIME, at least 28 days before she starts taking lenalidomide. FCBP must also agree to ongoing pregnancy testing. Men must agree to use a latex condom during sexual contact with a FCBP even if they have had a successful vasectomy.

[†]A female of childbearing potential is a sexually mature female who: 1) has not undergone a hysterectomy or bilateral oophorectomy; or 2) has not been naturally postmenopausal for at least 24 consecutive months (i.e., has had menses at any time in the preceding 24 consecutive months).

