8.0 PRETREATMENT EVALUATION

- A complete history and physical examination with documentation of measurable disease and assessment of performance status using the ECOG scale must be performed within 4 weeks prior to study entry
 - Patients will be evaluated for baseline neuropathy. Patients with grade 2 with painful neuropathy or grade 3 and higher will be excluded.

The following laboratory tests will be completed 4 weeks prior to study entry

- CBC with differential and reticulocyte count
- Chem 14, Magnesium, and Phosphate and eGFR determination
- Uric acid, LDH, and Beta-2 Microglobulin
- PT, PTT
- Serum protein electrophoresis (SPEP) and immunofixation to assess for presence and quantity of monoclonal protein (M-protein)
- 24-hour urine sample for protein electrophoresis (UPEP) and immunofixation to assess for monoclonal protein in the urine (Bence-Jones proteinuria) at baseline.
- Serum free light-chain studies, determined using the Freelite™ assay system
- Quantitative immunoglobulins

- Viral serologies
 - Hepatitis B surface antigen (HBsAg)
 - Hepatitis B surface antibody (Anti-HBs)
 - Hepatitis B core antibody (Anti-HBc)
 - Anti-Hepatitis C (HCV) antibody. If positive, will follow with HCV RNA PCR
 - HIV antibodies 1 & 2
- Review of bone marrow core biopsy and aspirate.
- Serum or urine pregnancy test in women of child-bearing potential.
- 12-lead EKG
- Echocardiogram
- Daratumumab Type and Screen Immunotherapy
- Stool sample collection

HBV Serology

Additionally, subjects ongoing in the Treatment Phase who are within 6 months of starting study treatment when Protocol Amendment 7 is implemented will be required to have HBV serology performed locally upon signing the updated ICF.

HBV serology is not required at Screening or for subjects ongoing in the Treatment Phase who are within 6 months of starting study treatment if this was performed as part of standard of care within 3 months prior to first dose.

HBV DNA Tests:

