9.0 TREATMENT/INTERVENTION PLAN

Patients who have signed the consent form and are deemed eligible for this clinical trial will start therapy with the following schedule:

- Length of cycle: 28 days. Treatment window for day 1 of start of each cycle is +/- 7 days. Treatment window for intra-cycle carfilzomib and/or daratumumab doses is +/- 2 days.
- These cycles will consist of:

Cohort 1

- Cycle 1 ONLY: Daratumumab 16 mg/kg days 1, 8, 15, and 22; Carfilzomib 20 mg/m² per dose, days 2 and 3; Carfilzomib 36 mg/m² per dose, days 8, 9, 15, and 16; Dexamethasone 20 mg/dose, days 1, 2, 3, 8, 9, 15, 16 and 22; Lenalidomide 25 mg/day, days 2 – 21 every 28 days; Acetaminophen 650 mg; intravenous Diphenhydramine 25 mg. Montelukast 10 mg will be administered prior to the first 4 doses of Daratumumab.
- Cycle 2: Daratumumab 16 mg/kg days 1, 8, 15, and 22; Acetaminophen 650 mg; intravenous Diphenhydramine 25 mg.
- Cycles 3-6: Daratumumab 16 mg/kg days 1 and 15; Acetaminophen 650 mg; intravenous Diphenhydramine 25 mg.
- Cycles 7-8: Daratumumab 16 mg/kg day 1; Acetaminophen 650 mg ; intravenous Diphenhydramine 25 mg.
- Cycles 2-8: Carfilzomib 36 mg/m² per dose, days 1, 2, 8, 9, 15, and 16
- Cycles 2-8: Lenalidomide 25 mg/day, days 1-21 every 28 days
- Cycles 2: Dexamethasone 20 mg/dose, days 1, 2, 8, 9, 15, 16 and 22
- Cycles 3-4: Dexamethasone 20 mg/dose, days 1, 2, 8, 9, 15 and 16
- Cycles 5- 8: Dexamethasone 10 mg/dose, days 1, 2, 8, 9, 15 and 16

Cohort 2

- Cycle 1 ONLY: Daratumumab 16 mg/kg days 1, 8, 15, and 22; Carfilzomib 20 mg/m² per dose, day 2; Carfilzomib 56 mg/m² per dose, days 8 and 15; Dexamethasone 20 mg/dose, days 1,2, and 22, 40 mg/dose days 8 and 15 ; Lenalidomide 25 mg/day, days 2–21 every 28 days; Acetaminophen 650 mg; intravenous Diphenhydramine 25 mg. Montelukast 10 mg will be administered prior to the first 4 doses of Daratumumab.
- Cycle 2: Daratumumab 16 mg/kg days 1, 8, 15, and 22; Acetaminophen 650 mg; intravenous Diphenhydramine 25 mg.

- Cycles 3-6: Daratumumab 16 mg/kg days 1 and 15; Acetaminophen 650 mg; intravenous Diphenhydramine 25 mg.
- Cycles 7-8: Daratumumab 16 mg/kg day 1; Acetaminophen 650 mg; intravenous Diphenhydramine 25 mg.
- Cycles 2-8: Carfilzomib 56 mg/m² per dose, days 1, 8, and 15
- Cycles 2-8: Lenalidomide 25 mg/day, days 1-21 every 28 days
- Cycles 2: Dexamethasone 40 mg/dose, days 1, 8, and 15; 20 mg/dose day 22
- Cycles 3-4: Dexamethasone 40mg/dose, Days 1, 8 15
- Cycles 5-8: Dexamethasone 20mg/dose, Days 1, 8, 15

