9.3 Non-Hematologic Toxicities Requiring Dosing Modifications

- 9.3.1 Any \geq Grade 3 toxicity require appropriate study drug to be held until resolved to Grade 1 or baseline (unless specified below in tables 9.4.4) prior to resuming therapy or initiating next cycle. Investigator will determine which drug will be held based on side effect profile and clinical judgment. If therapy has been held for more than 2 weeks due to non-hematologic toxicity, the patient will be removed from protocol therapy.

- 9.3.2 Protocol therapy will be withheld for patients who require treatment of Grade 3 infection. If therapy has been held for more than 3 weeks due to treating a grade 3 infection, the patient will be removed from protocol therapy.
- 9.3.3 For patients experiencing \geq grade 3 toxicity (unless specified below in tables 9.4.4), subsequent doses will be reduced at next dose level (according to the tables in section 9.2) if the adverse event was deemed to be attributed to study drugs. If the adverse event was deemed to be unrelated to study drugs, the patient may continue the full dose.
- 9.3.4 Electrolyte or metabolic abnormalities that are reversible with electrolyte replacement within 48 hours or $<$ grade 3 infections that can be controlled by appropriate therapy are exempt from holding treatment or dose modifications.

Lenalidomide Toxicities	Specific Dosing Modifications
Blistering Rash (Any Grade)	Discontinue lenalidomide and remove patient from therapy
Venous thrombosis/embolism	Hold lenalidomide and start therapeutic anticoagulation. Restart lenalidomide at investigator's discretion at current dose level.
Renal Dysfunction CrCl based on Cockcroft-Gault formula: $\text{CrCl} = (140 - \text{Age}) \times \text{Mass (in kilograms)} \times [0.85 \text{ if Female}] \div 72 \times \text{Serum Creatinine (in mg/dL)}$	
 CrCl 31-60 mL/min – Dose reduce lenalidomide to 10 mg daily from Days 1-21 CrCl ≤ 30 mL/min (not requiring dialysis) – Dose reduce Lenalidomide to 15 mg every 48 hours CrCl ≤ 30 mL/min (requiring dialysis) – Decrease Lenalidomide to 5 mg daily and on dialysis days give lenalidomide dose after dialysis.
Infection (\geq Grade 3)	
Hold therapy, treat underlying infection.
 
Remove patient from therapy if treatment of grade 3 infection persists for more than 3 weeks.

Carfilzomib Toxicities	Specific Dosing Modifications

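### Renal eligibility and the lenalidomide renal rule use different estimators and both include 60 mL/min, and the plan does not say whether the dose rule applies to a baseline value

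*Combined protocol and SAP*

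**What the plan says.** **Eligibility (Section 6.1).** The criterion is "Creatinine Clearance ≥ 60 ml/min", followed by "CrCl can be measured or estimated using Cockcroft-Gault method, MDRD, or CKD-EPI formulae". No order of priority is given among the four routes. The screening tests in Section 8.0 include "Chem 14, Magnesium, and Phosphate and eGFR determination", without naming an equation.

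**Starting dose (Section 9.0).** Both cohorts receive lenalidomide 25 mg/day on days 2 to 21 of cycle 1. From then on the line is "Cycles 2-8: Lenalidomide 25 mg/day, days 1-21 every 28 days". Neither line carries a renal condition. The same schedule appears in Section 1.0, Section 4.2 and footnote p of the Section 10.0 calendar.

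**Renal dose rule (Section 9.3, lenalidomide toxicities table).** The renal dysfunction row is "CrCl based on Cockcroft-Gault formula" and prints that formula. Its top band is "CrCl 31-60 mL/min", with the instruction "Dose reduce lenalidomide to 10 mg daily from Days 1-21". The row does not say whether it covers a value present at baseline or only a decline on treatment.

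**The concern.** The rule that admits a patient and the rule that sets the lenalidomide dose do not measure renal function in the same way, and they share the value 60. A patient can be properly enrolled and still satisfy the literal condition of the 10 mg row before or soon after the first capsule, with no change in renal function.

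This is first a dosing and safety matter. The table attaches a different dose to a clearance that the eligibility rule, by another formula, accepts at the full starting dose. It also bears on how lenalidomide exposure and the toxicity summaries by grade and cycle (Section 14.0) are read. Exposure could depend on which formula a prescriber used, and a reduction could be recorded as renal toxicity when only the estimator had changed.

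**Working it through.** The plan states no figure to reproduce here. The check compares the rules and evaluates the formulae.

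**1. The value 60, from the documents alone.** Eligibility is CrCl ≥ 60, and the reduction band is 31 to 60 with its end included as written. The Section 9.3 formula, reading 72 × creatinine as the denominator, is

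CrCl = (140 − age) × kg × (0.85 if female) / (72 × SCr).

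A man of 80 years, 72 kg, SCr 1.0 mg/dL: (60 × 72)/(72 × 1.0) = 60.0. He is eligible and also in the 10 mg band, with one formula used throughout.

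**2. Different estimators.** The documents do not print MDRD or CKD-EPI. As an assumption, I used the standard equations without a race term:

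- MDRD = 175 × SCr^−1.154 × age^−0.203 × (0.742 if female).
- CKD-EPI 2009 = 141 × min(SCr/k, 1)^a × max(SCr/k, 1)^−1.209 × 0.993^age × (1.018 if female), with k = 0.7, a = −0.329 for women and k = 0.9, a = −0.411 for men.
- CKD-EPI 2021 = 142 × min(SCr/k, 1)^a × max(SCr/k, 1)^−1.2 × 0.9938^age × (1.012 if female), same k, with a = −0.241 for women and −0.302 for men.

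First row below, Cockcroft-Gault: (140 − 80) × 50 × 0.85 / (72 × 0.8) = 2550/57.6 = 44.3. The CKD-EPI column runs from the 2009 to the 2021 version.

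| Patient | Cockcroft-Gault | MDRD | CKD-EPI |
|---|---|---|---|
| Woman 80 y, 50 kg, 0.8 mg/dL | 44.3 | 69.0 | 69.6–74.4 |
| Woman 75 y, 50 kg, 0.9 | 42.6 | 61.0 | 62.5–66.7 |
| Woman 70 y, 60 kg, 0.9 | 55.1 | 61.9 | 64.8–68.8 |
| Man 78 y, 65 kg, 1.0 | 56.0 | 72.3 | 71.8–77.0 |
| Man 70 y, 60 kg, 1.0 | 58.3 | 73.9 | 75.9–81.0 |
| Man 60 y, 70 kg, 1.0 | 77.8 | 76.2 | 81.4–86.2 |

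The first five patients are eligible by MDRD or CKD-EPI and lie in the 31 to 60 band by Cockcroft-Gault. The sixth shows no conflict. Weight enters Cockcroft-Gault and not the other two, so the divergence is mainly in lighter, older patients. Section 6.1 sets no upper age limit and no lower weight limit.

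**3. Whether the row reaches cycle 1.** The row is triggered by a clearance level. In the carfilzomib table of the same section, the neuropathy row is limited to treatment-emergent events; the renal row has no such limit. Section 9.4.1 repeats the chemistry panel on days 1, 2, 8, 15 and 22 of cycle 1. No baseline Cockcroft-Gault value is required. A patient enrolled by CKD-EPI with a Cockcroft-Gault value of 44 will show 44 again at the next draw if nothing changes, and nothing in the plan separates that from a decline. The day 1 criteria in Section 9.2 cover only neutrophils and platelets.

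**4. Size of the divergence in cycle 1.** Treatment plan: 25 mg × 20 days = 500 mg. Renal row: 10 mg × 21 days = 210 mg, or 10 mg × 20 days = 200 mg if kept to days 2 to 21. The ratio is 200/500 = 40% to 210/500 = 42%.

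**The case against.** The strongest answer is that the renal row belongs to a section on toxicities that require dose changes, is labelled as renal dysfunction, and is phrased as a reduction. Read in place, it manages dysfunction that develops on treatment, and cycle 1 then has one dose, 25 mg. This reading is fair, and it makes a cycle 1 conflict possible rather than certain. It does not close the question. The row has no onset condition, and without a baseline value by the same formula the on-treatment reading cannot be applied to the repeat labs.

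Other limits also stand. The overlap at 60 affects only that exact value. The examples were chosen to show divergence and rest on outside equations, and the sixth patient shows that it is not general. It would go too far to say that the eligibility filter fails to screen out renal impairment as the table defines it; it does so only for patients whose estimates straddle 60.

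A reader might infer two further things that the documents do not support:

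- *Sites would dose differently.* Section 7.0 places the study at one centre, so the divergence is between prescribers.
- *Reduced-dose patients contaminate an MRD rate for full-dose treatment.* Section 14.0 counts as evaluable anyone who receives any study drug and has a post-baseline disease assessment, and Section 9.1.1 allows lenalidomide reductions down to 5 mg. No full-dose population is defined.

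**Conclusion.** The concern holds as an unresolved inconsistency in a dosing instruction. Three facts come from the documents alone: eligibility accepts four routes while the lenalidomide rule accepts one, both rules include 60, and the renal row does not say whether it applies to a baseline value. That eligible patients can lie well inside the 31 to 60 band rests on the assumed MDRD and CKD-EPI equations; the gap is about 7 to 30 mL/min in the five affected examples. If the row is applied from cycle 1, the dose in that cycle is 40% to 42% of the scheduled amount.

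The documents do not support the stronger statement that every such patient has two contradictory doses at cycle 1, because the on-treatment reading remains open. The share of patients affected cannot be derived. The Simon design and its error rates are unaffected. The point still needs correction before it is left to individual prescribers, because it bears on patient safety and is cheap to settle.

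**What to change.** Reconcile Section 6.1, Section 9.0 (with the parallel schedules in Sections 1.0, 4.2 and 10.0) and the renal row of Section 9.3 on three points:

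1. State which estimator governs both eligibility and lenalidomide dosing. Alternatively, keep the present eligibility routes and require a recorded baseline value by the Section 9.3 formula, so that later values can be compared with it.
2. Make the eligibility threshold and the upper edge of the band mutually exclusive, so that 60 falls on one side only.
3. State whether the renal row applies to a value present at cycle 1 day 1 or only to a decline on treatment, and, if the latter, a decline from what.

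The dose, the cut-off and the formulae that remain are for the sponsor to decide. Deleting the alternative formulae is not required, and it would also raise the question of measured clearance.

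The cost is amendment wording. Age and creatinine are already available, and weight is needed for the mg/kg daratumumab dose. A few borderline patients may be reclassified, depending on the sponsor's choice.

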6.2 Subject Exclusion Criteria

- Patients receiving >1 cycle of prior treatment or concurrent systemic treatment for multiple myeloma
 - Treatment of hypercalcemia or spinal cord compression or aggressively progressing myeloma with current or prior corticosteroids is permitted
 - Bisphosphonates are permitted
 - Concurrent or prior treatment with corticosteroids for indications other than multiple myeloma is permitted
 - Prior treatment with radiotherapy is permitted
 - Prior treatment for smoldering myeloma is permitted with a washout period of 2 weeks from last dose. Smoldering patients previously treated with carfilzomib are excluded.
 - Patients with measurable disease who received up to one cycle of any therapy within 60 days with a washout period of 2 weeks from last dose (on a trial or outside a trial) are eligible
- Plasma cell leukemia
- POEMS syndrome
- Amyloidosis

- Has known chronic obstructive pulmonary disease with a forced expiratory volume in 1 second (FEV1) <50% of predicted normal (note that FEV1 testing is required for subjects suspected of having chronic obstructive pulmonary disease and subjects must be excluded if FEV1 <50% of predicted normal).
- Pregnant or lactating females. Because there is a potential risk for adverse events nursing infants secondary to treatment of the mother with carfilzomib in combination with lenalidomide. These potential risks may also apply to other agents used in this study.
- Uncontrolled hypertension or diabetes
- Active hepatitis B or C infection
- Subject is:
 - Seropositive for human immunodeficiency virus (HIV)
 - Seropositive for hepatitis B (defined by a positive test for hepatitis B surface antigen [HBsAg]). Subjects with resolved infection (i.e., subjects who are HBsAg negative but positive for antibodies to hepatitis B core antigen [anti-HBc] and/or antibodies to hepatitis B surface antigen [anti-HBs]) must be screened using real-time polymerase chain reaction (PCR) measurement of hepatitis B virus (HBV) DNA levels. Those who are PCR positive will be excluded. EXCEPTION: Subjects with serologic findings suggestive of HBV vaccination (anti-HBs positivity as the only serologic marker) AND a known history of prior HBV vaccination, do not need to be tested for HBV DNA by PCR.*
 - Seropositive for hepatitis C (except in the setting of a sustained virologic response [SVR], defined as aviremia at least 12 weeks after completion of antiviral therapy).
- Has significant cardiovascular disease with NYHA Class III or IV symptoms, EF \leq 40% or hypertrophic cardiomyopathy, or restrictive cardiomyopathy, or myocardial infarction within 6 months prior to enrollment, or unstable angina, or unstable arrhythmia as determined by history and physical examination. Echocardiogram will be performed during screening evaluation.
- Pulmonary hypertension
- Has refractory GI disease with refractory nausea/vomiting, inflammatory bowel disease, or bowel resection that would prevent absorption of oral agents

- Uncontrolled intercurrent illness including but not limited to active infection or psychiatric illness/social situations that would compromise compliance with study requirements
- Significant neuropathy \geq Grade 3 or Grade 2 neuropathy with pain at baseline
- Contraindication to any concomitant medication, including antivirals or anticoagulation.
- Major surgery within 3 weeks prior to first dose

7.0 RECRUITMENT PLAN

This study will be conducted at MSKCC. Efforts will be made to ensure that women and minority groups are adequately represented in this trial. All patients will be seen by a myeloma physician and associated study co-investigator, enrolled and registered at MSKCC. All co-investigators agree to follow the treatment in the protocol and to conduct the proposed investigation according to recognized principles of good clinical practice. Participation is voluntary. Each patient must be informed about the neoplastic nature of his/her disease and willingly consent to participation in this study. Every patient will be informed of the procedures to be followed, the potential benefits, side effects, risks, and discomforts of the trial and of potential therapeutic alternatives. All participants will be required to sign statements of informed consent and research authorization that conform to FDA, IRB and HIPAA guidelines. Informed consent will be documented by the use of a written consent form that has been approved by the MSKCC IRB.

8.0 PRETREATMENT EVALUATION

- A complete history and physical examination with documentation of measurable disease and assessment of performance status using the ECOG scale must be performed within 4 weeks prior to study entry
 - Patients will be evaluated for baseline neuropathy. Patients with grade 2 with painful neuropathy or grade 3 and higher will be excluded.

The following laboratory tests will be completed 4 weeks prior to study entry

- CBC with differential and reticulocyte count
- Chem 14, Magnesium, and Phosphate and eGFR determination
- Uric acid, LDH, and Beta-2 Microglobulin
- PT, PTT
- Serum protein electrophoresis (SPEP) and immunofixation to assess for presence and quantity of monoclonal protein (M-protein)
- 24-hour urine sample for protein electrophoresis (UPEP) and immunofixation to assess for monoclonal protein in the urine (Bence-Jones proteinuria) at baseline.
- Serum free light-chain studies, determined using the Freelite™ assay system
- Quantitative immunoglobulins

- Viral serologies
 - Hepatitis B surface antigen (HBsAg)
 - Hepatitis B surface antibody (Anti-HBs)
 - Hepatitis B core antibody (Anti-HBc)
 - Anti-Hepatitis C (HCV) antibody. If positive, will follow with HCV RNA PCR
 - HIV antibodies 1 & 2
- Review of bone marrow core biopsy and aspirate.
- Serum or urine pregnancy test in women of child-bearing potential.
- 12-lead EKG
- Echocardiogram
- Daratumumab Type and Screen Immunotherapy
- Stool sample collection

HBV Serology

Additionally, subjects ongoing in the Treatment Phase who are within 6 months of starting study treatment when Protocol Amendment 7 is implemented will be required to have HBV serology performed locally upon signing the updated ICF.

HBV serology is not required at Screening or for subjects ongoing in the Treatment Phase who are within 6 months of starting study treatment if this was performed as part of standard of care within 3 months prior to first dose.

HBV DNA Tests:

Subjects who are positive for Anti-HBc or Anti-HBs will undergo testing for hepatitis B DNA by PCR. Subjects with serologic findings suggestive of HBV vaccination (Anti-HBs positivity as the only serologic marker) and a known history of prior HBV vaccination do not need to be tested for HBV DNA by PCR. During and following study treatment, subjects who have history of HBV infection will be closely monitored for clinical and laboratory signs of reactivation of HBV as specified in the Time and Events Schedule (Section 10.0). Where required by local law, the results of HBV testing may be reported to the local health authorities.

Research and clinical laboratory tests to be performed within 4 weeks of study entry and prior to starting therapy

- Bone Marrow
 - Histopathological evaluation on bone marrow aspirate and biopsy
 - Immunophenotyping of aberrant clonal plasma cells by multiparametric flow cytometry.
 - Immunoglobulin heavy and/or light chain rearrangement.
 - Interphase FISH/cytogenetics
 - To create a bone marrow and peripheral blood sample bank of whole BM lysate, CD 138+ fractions and CD 138- fractions cell sorting with subsequent correlatives on both fractions. These samples may be used to later evaluate

biological activity of carfilzomib, lenalidomide, and dexamethasone. Potential analyses include sequencing and gene expression profiling on pre and post therapy bone marrow samples, identification of potential biomarkers (blood, urine, bone marrow aspirates), and evaluation of proteasome activity.

- Sample for NGS MRD should be bone marrow aspirate (not biopsy and not CD138 purified, per the assay validation) 1mL, frozen at -70°C.
- Patients who have completed 1 cycle of SOC therapy who meet eligibility criteria and have an HOTB sample at MSK within 60 days of cycle 1 day 1, will not need an additional bone marrow biopsy or aspirate, unless clinically indicated.
- Peripheral Blood/Urine
 - Peripheral blood and urine samples for storage and establishing a biobank.
 - Immune cells – including, but not limited to T cells (CD4 and CD8), LGL, and NK cells.
 - Indirect Coombs Test or other tests required by the local blood bank needed before treatment with CD38-antibodies.

Imaging (FDG/PET/CT scan) within 8 weeks of study entry and prior to starting therapy

Prior to ^{18}F -FDG PET/CT imaging, the subject will be fasted and have not received any sugar containing substance (i.e. glucose, sucrose, dextrose) for 4-6 hours. Subjects will be encouraged to drink water during this period to reduce radiation dose to the kidneys and will be asked to void prior to ^{18}F -FDG injection. Women of childbearing potential will have a documented report of negative pregnancy test from the CC or another accredited lab performed on the day of the scan or the day before the scan.

^{18}F -FDG, [18F]-fludeoxyglucose is an FDA approved radiopharmaceutical. Immediately prior to injection, the subject's blood glucose level will be evaluated via fingerstick. Non-diabetic subjects with fasting blood glucose levels above 150 mg/dl may be rescheduled at the discretion of the PI. Subjects will be asked to refrain from excessive physical exertion for the 24 hours prior to injection. The ^{18}F -FDG injection procedure will be injected and be followed by a ~20 ml saline (sodium chloride IV infusion 0.9% w/v) flush over a period of ~20 seconds. The injection site will be evaluated pre- and post administration for any reaction (e.g. bleeding, hematoma, redness, or infection).

Whole body (vertex to toes) static PET/CT imaging will be performed beginning at 1-hour, and again at 2-hours post injection. PET/CT standard operating procedures. The patient will be instructed to maintain good hydration in order to reduce the radiation dose.

The radiation dose from the procedure will be a maximum of 2.1 rem per year; this is within the RSC guidelines of 5.0 rem per year for adults.

PET-CT performed within the 8 weeks at an outside institution can be acceptable as baseline study as long as films are forwarded to the Department of Radiology for an official MSKCC reading. Patients who have completed 1 cycle of SOC therapy who meet eligibility criteria and have had a PET scan read at MSK within 60 days of cycle 1 day 1, will not need an additional PET scan, unless clinically indicated

